8.1.5.1.2. Accumulation Ratio

Part 1

Predidicted daily dose accumulation from single dose data (Part 1) for AUC will be as follows:

$$Rp(AUC) = \frac{AUC(0 - \infty)}{AUC(0 - 24)}$$

Point estimates of the mean ratio and associated 90% confidence intervals will be displayed by treatment.

Part 2

Accumulation will also be evaluated for each treatment by determining the ratio of Day 14 (Part 2 cohort 3 and 4) or Day 18 (Part 2 cohort 5) to Day 1 AUC(0- τ) (R(AUC(0- τ)), Cmax (R(Cmax)), and C τ (R(C τ)). Day 1 C τ will be defined as the 24-hr post day 1 dosing concentration (C24 for Day 1). For part 2 cohort 3,4, and 5 the dosing interval is 24-hrs. Therefore, $\tau=24$ hrs.

For Cohort 6 accumulation will be evaluated by determining the ratio of third dose (occurring on Day 15) to first dose (Day 1) for AUC(0- τ) (R(AUC(0- τ)), Cmax

(R(Cmax)), and C τ (R(C τ)). For part 2 cohort 6 the dosing interval is 7 days (168 hrs). Therefore, $\tau=168$ hrs. In Cohort 6, since sampling at 168 hrs post 3rd dose was not collected, it will be predicted using linear model based on the other collected timepoints post dose.

Point estimates of the mean ratios and associated 90% confidence intervals will be displayed by treatment.

Endpoint / Variables

 • Rp(AUC) for Part 1 Where $Rp(AUC) = \frac{AUC(0 - \infty)}{AUC(0 - 24)}$ • R(AUC(0-τ)), R(Cmax), R(Cτ) on Days 1 and 14 for Part 2 Cohort 3 and 4 where, $\tau=24$ hrs • R(AUC(0-τ)), R(Cmax), R(Cτ) on Days 1 and 18 for Part 2 Cohort 5 where, $\tau=24$ hrs • R(AUC(0-τ)), R(Cmax), R(Cτ) on Days 1 and 15 for Part 2 Cohort 6 where, $\tau=168$ hrs 
Where
 $R(Parameter) = \frac{(Parameter\ Value\ on\ Day\ XX)}{(Parameter\ Value\ on\ Day\ 1)}$
Model Specification

 • In Part 1 the mean of the raw mean of the ratio of AUC(0-inf) to AUC(0-24) will be reported. There is no formal modeling. • In the model for Part 2 Cohort 3,4,5,6 the ratio of the specific parameter will be the dependent variable, day will be included as a fixed effect categorical variable with the reference as Day 1, and participant will be included as a random effect.
Model Checking & Diagnostics

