
 • A compound symmetry covariance structure for the R matrix will be used by specifying "type=CS" on the RANDOM line • In the event that this model fails to converge, alternative correlation structures may be considered such as CSH. • The Kenward and Roger method for approximating the denominator degrees of freedom and correcting for bias in the estimated variance-covariance of the fixed effects will be used. • Normality assumptions underlying the model used for analysis will be examined by obtaining a normal probability plot of the residuals and a plot of the residuals versus the fitted values (i.e. checking the normality assumption and constant variance assumption of the model respectively) to gain confidence that the model assumptions are reasonable. • If there are any departures from the distributional assumptions, alternative models will be explored using appropriate transformed data.

Model Results Presentation

 For Part 1, point estimates of the means of AUC(0-inf) and AUC(0-24), the point estimate of the predicted accumulation ratio, and the associated 90% confidence interval will be presented in tabular format by treatment group. For Part 2, point estimates of the Geometric least squares means and 90% confidence intervals for the accumulation ratio will be presented in tabular format by treatment group.
Subgroup Analyses

 Not Applicable.
Sensitivity and Supportive Analyses

 Not Applicable.

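### The Part 2 accumulation model takes the Day XX/Day 1 ratio as its outcome and also fits day against Day 1; the outcome should be the log PK parameter

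*SAP*

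**What the plan says.** SAP 8.1.5.1.2 defines R(Parameter) as the value on Day XX over the value on Day 1, for AUC(0-τ), Cmax and Cτ. It lists the ratios "on Days 1 and 14 for Part 2 Cohort 3 and 4 where" τ is 24 h, with Days 1 and 18 for Cohort 5 and Days 1 and 15 for Cohort 6. In the model for all four cohorts "the ratio of the specific parameter will be the dependent variable, day will be included as a fixed effect categorical variable". Day 1 is named as the reference level, and participant enters as random.

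The supporting text adds three things:
- Covariance: "A compound symmetry covariance structure for the R matrix will be used by specifying" an option on the RANDOM line, with "The Kenward and Roger method for approximating the denominator degrees of freedom". It continues: "In the event that this model fails to converge, alternative correlation structures may be considered such as CSH".
- Diagnostics: normal probability and residual-versus-fitted plots. "If there are any departures from the distributional assumptions, alternative models will be explored using appropriate transformed data".
- Output: "point estimates of the Geometric least squares means and 90% confidence intervals for the accumulation ratio", by treatment group.

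The model specification names no log transformation. The Part 3 model in SAP 8.1.5.1.4 does name one. Protocol 9.4.4 asks for the ratio to Day 1 and prescribes no model for it.

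**The concern.** A day effect with Day 1 as reference makes sense when the outcome is the PK parameter, because the day contrast is then the accumulation. Here the outcome has already been divided by Day 1, so the reference level carries no information and no variance.

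Accumulation is a secondary objective of both documents. Three things are left to the programmer: whether Day 1 rows are in the data set, whether the ratio is logged, and whether the reported interval belongs to the later-day least squares mean or to its contrast with Day 1. These choices change both the quantity estimated and the coverage of its interval.

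**Working it through.** The documents give no precision or coverage figure for this analysis, so there is nothing to reproduce first.

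**Inputs**
- n = 7 active per Part 2 cohort (SAP 2.3, Protocol 4.1).
- Two-sided 90% interval, compound symmetry, Kenward-Roger degrees of freedom (SAP 8.1.5.1.2).
- Anticipated accumulation of about 6-fold daily and 1.3-fold weekly (Protocol 4.1), used only as a centre.
- CV of the individual ratio: an assumption, because none is given for Part 2. Carrying over the 25% within-subject CV that Protocol 9.2.1 uses for Part 3, each day has log variance ln(1 + 0.25²) = 0.0606. The ratio of two days has twice that, 0.1213, so its CV is √(exp(0.1213) − 1) = 36%. I varied it from 15% to 50%.

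**Step 1: the two possible data layouts**
- Day 1 and Day XX rows: all 7 Day 1 outcomes equal 1 (0 if logged).
- Day XX rows only: day has one level, the stated reference does not exist, and with one row per participant the participant variance cannot be separated from error. The model cannot be fitted as written.

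**Step 2: literal fit of the first layout, log scale**
Let s be the SD of the 7 Day XX log-ratios. REML pools a day with variance 0 and a day with variance s²:
- participant variance = 0 and residual variance = (0 + s²)/2 = s²/2;
- SE of the Day XX least squares mean = √(s²/2 ÷ n) = s/√(2n);
- SE of the Day XX minus Day 1 contrast = √(2 × s²/2 ÷ n) = s/√n.

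Numerical mixed-model fits to simulated data agreed. In one, the residual variance was 0.02173 against s²/2 = 0.02173, and the two SEs were 0.05572 and 0.07879 against 0.05572 and 0.0788.

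**Step 3: interval of the Day XX least squares mean**
Degrees of freedom are 2(n − 1) = 12, so t = 1.78. The correct interval uses s/√n with 6 df, t = 1.94. The width ratio is 1.78 ÷ (1.94 × √2) = 0.65, so the interval is about 35% too narrow. Coverage is P(|t₆| < 1.78/√2) = 74.6%, whatever the SD. With 6 or 5 evaluable participants it is 74.4% or 74.1%.

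**Step 4: interval of the contrast with Day 1**
The SE is right. Coverage is 90.0% with 6 df (covariance parameter kept) and 87.5% with 12 df (parameter dropped at zero).

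**Step 5: the ratio left untransformed**
The contrast now estimates R − 1: about 5 where R is 6, and 0.3 where R is 1.3. Coverage (%) of the geometric mean ratio, from 200,000 simulated trials per row, with 1 added back to the contrast:

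| Ratio CV | LS mean, 12 df | Contrast, 6 df | Contrast, 12 df |
|---|---|---|---|
| 15% | 74.1 | 90.0 | 87.5 |
| 25% | 73.6 | 90.0 | 87.4 |
| 35% | 72.7 | 89.9 | 87.2 |
| 50% | 71.3 | 89.9 | 87.0 |

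On this scale the point estimate is an arithmetic mean. For lognormal ratios it exceeds the geometric mean by the factor √(1 + CV²): 1.1%, 3.1% and 5.9% at CV 15%, 25% and 35%.

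**Step 6: what this looks like**
Take R = 6 and ratio CV 36%, so s = √0.1213 = 0.348.
- Correct log-scale interval: half-width 1.94 × 0.348/√7 = 0.256, giving about 4.6 to 7.7.
- Least-squares-mean interval: half-width 1.78 × 0.348/√14 = 0.166, giving about 5.1 to 7.1.

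**Step 7: the conventional model**
With the log PK parameter as outcome on both days, day fixed and participant random, the exponentiated day contrast covers 90.0% at n = 7. With complete data this is the paired t interval on the log ratios.

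**The case against.** The strongest reply is that the dependent variable has simply been misnamed. Categorical day, Day 1 as reference, participant random and geometric least squares means are the parts of a log-parameter model whose day contrast is the accumulation ratio. Part 3 uses the same covariance text and does state the log. If the team programs that model, nothing is lost. Even in the literal fit, naming Day 1 as reference points to the contrast, which loses little or no coverage. The residual plot would show every Day 1 residual at zero, and the SAP then permits other models. The analysis is estimation only, Part 2 was sized on feasibility, dose escalation uses a separate Bayesian model, and derived PK parameters are listed by participant, so a correct ratio can be recovered.

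Most of this stands, and it limits the size of the problem. It does not supply a correct model:
- The text says ratio in the definition, the endpoint list and the model.
- Logging the ratio leaves Day 1 constant at 0.
- The diagnostics act only after data are seen, and the replacement model is not named.
- The table shell that would show which interval is reported (PK_T4) is not in the documents, which say shells are available on request.

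A reader might also infer that the covariance wording is an error with consequences, since it puts an R-matrix structure on the RANDOM line and offers a richer fallback. The documents do not support giving this weight. The fallback is permissive, and no effect of the RANDOM wording on a result has been shown.

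**Conclusion.** The model is wrong as written and should be corrected, but it is not a defect that endangers the trial.

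The size depends on what is reported. With 7 participants per cohort, a nominal 90% interval covers about 72-75% if it is the interval of the later-day least squares mean (71.3% at a ratio CV of 50%). It covers about 87-90% if it is the contrast with Day 1, and on the raw-ratio scale that contrast is R − 1. The log-scale figures assume normal log-ratios and do not depend on the CV. The raw-scale figures rest on assumed ratio CVs.

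A reader might infer that the accumulation intervals will cover only about three quarters of the time in any case, or that the analysis must either fail or report an arithmetic mean. The documents do not support either. The low coverage belongs to one of two admissible readings of the output sentence, and the word geometric implies a log analysis that the model specification omits.

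**What to change.** Replace the Part 2 model sentence in SAP 8.1.5.1.2 with a specification along these lines:
- The dependent variable is the log-transformed PK parameter (AUC(0-τ), Cmax or Cτ), with one row for Day 1 and one for Day 14 (Cohorts 3 and 4), Day 18 (Cohort 5) or Day 15 (Cohort 6).
- Day is a fixed effect and participant a random intercept, fitted separately by cohort.
- The exponentiated later-day minus Day 1 difference and its 90% interval are reported as the geometric mean accumulation ratio.
- If the model does not converge, use the paired t interval on the log ratios.

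The output sentence should say that the interval is that of the day contrast. The cost is a few lines of SAP text and a check of the table shell. No new data are needed.

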8.1.5.1.3. Assessment of Steady State

For Part 2 cohorts 3 and 4, steady-state VH3739937 concentrations will be assessed by estimating the slope of concentrations on pre-dose assessments on Days 2-14 (Part 2 cohort 3 and 4) and the day 15 24-hr post-dose (relative to dosing on day 14). For Part 2 cohort 5, steady state VH37339937 concentrations will be assessed by estimating the slope of the concentrations of pre-dose assessments on Days 2-18 and the day 19 24-hr post-dose (relative to dosing on day 18).

To determine when steady state is achieved the separate mixed effects linear regression models will be estimated for each treatment and each subset of days. The first subset of days will include all $C\tau$ values for days 2-15. Then the value from the earliest timepoint will be dropped and the analysis re-run. Earlier days will be iteratively dropped (e.g. Days 2-15, then Days 3-15, then Days 4-15, etc.) until only 3 dosing days, and the 24-hr post final dose assessment, remain. The final assessment of the slope will be determined by at least the last 3 pre-dose concentrations and the concentration 24 hours post last dose.

Endpoint / Variables

 $C\tau$ Day (2-15) for Part 2 Cohort 3 and 4 $C\tau$ Day (2-19) for Part 2 Cohort 5
Model Specification

 In the model for Part 2 Cohort 3 and 4, $C\tau$ Day (2-15) will be the dependent variable, day will be included as a fixed effect, and participant will be included as a random effect In the model for Part 2 Cohort 5, $C\tau$ Day (2-19) will be the dependent variable, day will be included as a fixed effect, and participant will be included as a random effect
Model Checking & Diagnostics

 Normality assumptions underlying the model used for analysis will be examined by obtaining a normal probability plot of the residuals and a plot of the residuals versus the fitted values (i.e. checking the normality assumption and constant variance assumption)

of the model respectively) to gain confidence that the model assumptions are reasonable.
 
 • If there are any departures from the distributional assumptions, alternative models will be explored using appropriate transformed data.
Model Results Presentation

 • Point estimates and 90% confidence intervals for the slope will be presented in tabular format by treatment group. The analysis will be conducted for all days (2-15 for Cohort 3 and 4 and 2-19 for Cohort 5) and repeated by dropping one earlier day at a time until the final 3 days of dosing remain (that is days 12-14 and day 15 for cohort 3 and 4 and days 16-18 and day 19 for cohort 5). • Individual values of C_{τ} Day (2-15) for Part 2 Cohort 3 and 4 will be plotted graphically by treatment group • Individual values of C_{τ} Day (2-19) for Part 2 Cohort 5 will be plotted graphically by treatment group
Subgroup Analyses

 • Not Applicable.
Sensitivity and Supportive Analyses

 • Not Applicable.

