To characterize the population pharmacokinetics of VH3739937 and identify important determinants of variability, a population model was conducted as an alternate analysis approach to characterize the pharmacokinetics and the simulation was implemented to predicted the higher single dose and multiple dose cohort PK profile based on the model. The PK of VH3739937 following oral administration was adequately characterized by a linear one-compartment model with first-order absorption and first-order elimination, and with a dose factor and inter-individual variability on CL/F and on the magnitude of proportional residual error. The simulations for higher single dose 640 and 800 mg, multiple daily dose 50 and 100 mg and the multiple weekly dose 500 mg were conducted to predict the PK profile to obtain the Cmax and AUC for safety cover. More detailed information can be found in the Investigator's Brochure Supplement [GlaxoSmithKline Document Number [2021 RPS_CLIN_004025](#)].

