All participants will have a screening visit within 28 days prior to first dose and a follow-up visit approximately 28 days after the last dose. All dosing will be conducted in a hospital based inpatient clinical trial unit. Study participants will be confined to the clinic from Day -2 until discharge. Additional outpatient visits will be required for all study parts. Flexibility of visit scheduling may be required if a pandemic situation applies (see Appendix 7). Otherwise, study assessments will be performed as indicated in the SoA presented in this protocol.

A summary of the overall study design, including proposed doses, sample size, and order, is presented in Figure 3 and Figure 4 below.

Figure 3 Phase 1 Study in Healthy Participants using planned doses of VH3739937 Part 1 and Part 2

A=Active; P=Placebo

QD = once daily; QW = once weekly

*= Period 4 may include participants from both Cohorts 1 and 2

Highlighted cohorts and treatment periods denotes completed

The doses shown in [Figure 3](#) above are intended to demonstrate general concepts relating to factors of escalation. The modelling and simulation implemented using the data currently available following oral administration of a suspension formulation in the fed state indicated the predicted efficacious dose for the daily dose is 25 mg and the weekly dose is 500 mg. Due to the observed half-life of ~90 h, the anticipated accumulation ratio following repeated daily and weekly doses is ~6-fold and 1.3-fold, respectively. Dosing will be conducted in accordance with safety and PK stopping criteria (Section [7.1.4](#)).

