9.2. Sample Size Determination

9.2.1 Sample Size Assumptions

Parts 1 and 2

Sample size is based on feasibility. No formal calculation of power or sample size (i.e., sample size sensitivity or robustness) for Parts 1 and 2 of the study has been performed. A sample size of approximately 9 participants (6 active: 3 placebo) per dose-cohort should be sufficient to provide useful estimates of both inter- and intra-participant variability for VH3739937, PK parameters, and initial safety assessment.

Sample size re-estimation is not planned.

Data will be reviewed by the DEC prior to each dose escalation; no other interim analysis is planned.

Part 3

This is the first study which will evaluate the pharmacokinetic properties of VH3739937 in humans following oral administration of suspension and tablet formulations. Results from previous PK studies for GSK3640254 (a similar compound to VH3739937), and observed preliminary data from Part 1 of the study suggest that 25% is a conservative estimate for percent within subject coefficient of variation (%CVw) of Cmax and AUC(0-t) and will therefore be used to assess the precision (i.e. half width of the 90% confidence interval on the log and ratio scale) potential sample sizes of this three period crossover RBA/FE study. Assuming a within participant coefficient of variation of 25% and a sample size of 12 participants, it is estimated that the half width of the 90% confidence interval for the formulation difference on the log-scale will be within 0.173 of the point estimate (assumed to be 1.0). If the point estimate of the ratio of geometric means is assumed to be 1.0, then the 90% confidence interval will be approximately (0.841, 1.189) on the original scale.

Since tablet formulation and amount of food consumed may change the exposure to VH3739937, a range of point estimates for true ratio of 0.9, 1.0, and 1.1 were used in combination with sample sizes ranging from 12 to 18. The resulting estimated 90% confidence intervals are shown in [Table 13](#) below.

Table 13 90% Confidence Intervals for RBA/FE of VH3739937

n	%CVw	Point Estimate	90% CI
12	25	0.9	(0.757, 1.070)
12	25	1	(0.841, 1.189)
12	25	1.1	(0.925, 1.308)
15	25	0.9	(0.772, 1.049)
15	25	1	(0.858, 1.166)
15	25	1.1	(0.944, 1.282)
18	25	0.9	(0.783, 1.034)
18	25	1	(0.870, 1.149)
18	25	1.1	(0.957, 1.264)

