2.3. Study Design

Overview of Study Design and Key Features	
	
placebo (PBO) for 14 consecutive days (cohorts 3 and 4), or for 18 consecutive days (cohort 5). Participants in Cohort 6 will receive one dose per week for 3 consecutive weeks.
 
 • The duration of dosing in Cohort 5 is to support up to 18-day dosing as an oral lead in for the future SAD and MAD studies of the long acting formulation of VH3739937. This duration is to potentially allow the identification of any early drug hypersensitivity reactions (HSR) which may occur before the administration of the long acting formulation. • In each escalating dose cohort, 7 participants will be randomized to receive VH3739937 and 3 participants will be randomized to receive PBO 
Part 3 (RBA/FE)
 
 • Part 3 is a randomized, open-label, single-dose, 3-period crossover Cohort 7 to compare the RBA of the PiB formulation of VH3739937 with the tablet formulation and to assess the effect of food on the safety, tolerability and PK of the tablet formulation in healthy participants. • In Part 3, approximately 18 participants will be treated to ensure that 12 evaluable participants complete Cohort 7.

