13.10.6. Pharmacokinetic Tables

Pharmacokinetic: Tables					
No.	Population	GSK Standard / Example Shell	Title	Programming Notes	Deliverable [Priority]
PK Concentration					
4.1.	PK	PK01	Summary of VH3739937 Plasma Pharmacokinetic Concentration (ng/mL) -Time Data by Treatment	Page by part	SAC [1]
4.2.	PK	PK03	Summary of Derived VH3739937 Plasma Pharmacokinetic Parameters by Treatment		SAC [1],HL
4.3.	PK	PK05	Summary of Log-Transformed Derived VH3739937 Plasma PK Parameters by Treatment		SAC [1],HL
Dose Proportionality, Accumulation, and Steady State					
4.4.	PK	PK_T1	Summary Results of Single Dose Proportionality Assessment Using Power Model – Part 1	Stats output, Non-Standard Shell PK_T1 PK parameters: AUC(0-inf), AUC(0-t), Cmax	SAC
4.5.	PK	PK_T1	Summary Results of Multiple Dose Proportionality Assessment Using Power Model – Part 2	Stats output Non-standard shell PK_T1 PK parameters: AUC(0-inf), AUC(0- τ), Cmax	SAC
4.6.	PK	PK_T2	Summary Results of Steady State VH3739937 Concentrations Assessment – Part 2	Stats output Non-standard shell PK_T2 Use up to day 14 for cohort 3 and 4 and day 18 for cohort 5.	SAC

Pharmacokinetic: Tables					
No.	Population	GSK Standard / Example Shell	Title	Programming Notes	Deliverable [Priority]
				Add footnote: Ctrough was collected on days 2,3,4,6,8, 10,11,12,13,14,15 for cohort 3 and 4 and days 2,3,4,6,8, 10,11,12,13,14,15, 16, 17,18 for cohort 5. Use C_{τ} to determine steady state for daily dosing MAD. See example from Table 4.13 from study 207187	
4.7.	PK	PK_T3	Summary Results of VH3739937 PK Parameter Treatment Comparisons Predicted Accumulation Ratio- Part 1	Stats output, Non-Standard Shell at end of RAP Non-standard shell PK_T3	SAC
4.8.	PK	PK_T4	Summary Results of VH3739937 PK Parameter Treatment Comparisons Accumulation Ratio- Part 2	Stats output, Non-standard shell PK_T4 Add footnote: In Cohort 6, since sampling at 168 hrs (7 days) post 3 rd dose was not collected, it will be approximated by 192 hrs post dose.	SAC
Relative Bioavailability/Food Effect					
4.9.	PK	PK_T5	Summary of Result of Plasma VH3739937 Pharmacokinetic Parameter Treatment Comparisons for Relative Bioavailability	Stats output	SAC [1], HL

Pharmacokinetic: Tables					
No.	Population	GSK Standard / Example Shell	Title	Programming Notes	Deliverable [Priority]
				PK Parameters: $AUC_{(0-24)}$, $AUC_{(0-\infty)}$, and C_{max} Ratio: Test/Reference (Tablet/PiB) See study mid208131 Table 4.4 for reference Non-standard shell PK_T5	

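### The steady-state slope model allows participants different trough levels but not different rates of rise, so its 90% intervals are too narrow in the long and middle windows

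*SAP*

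**What the plan says.** SAP 8.1.5.1.3 covers Cohorts 3 to 5. It states that "separate mixed effects linear regression models will be estimated for each treatment and each subset of days". Starting from all sampled days, the earliest day is dropped one at a time until three dosing days and the sample 24 h after the last dose remain. For each fit, "day will be included as a fixed effect, and participant will be included as a random effect". On output: "Point estimates and 90% confidence intervals for the slope will be presented in tabular format by treatment group".

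The response is the untransformed trough. Transformation is considered only if residual plots show departures from normality or constant variance. The section names no participant-by-day term, covariance structure or degrees-of-freedom method. The neighbouring sections on accumulation (8.1.5.1.2) and relative bioavailability (8.1.5.1.4) do name compound symmetry and Kenward-Roger.

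Each daily cohort is small: "7 participants will be randomized to receive VH3739937 and 3 participants will be randomized to receive PBO" (SAP 2.3). The note to Table 4.6 in SAP 13.10.6 gives the sampling: "Ctrough was collected on days 2,3,4,6,8, 10,11,12,13,14,15 for cohort 3 and 4". Protocol 2.2.1 describes a one-compartment population model "with a dose factor and inter-individual variability on CL/F and on the magnitude of proportional residual error".

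**The concern.** A participant with lower clearance has a higher plateau and reaches it later, so that participant's trough slope is steeper. Once CL/F varies between people, slopes vary too, and the evidence about the average slope comes from 7 participants. A common-slope model with a random intercept absorbs differences in level but not in rate of rise. The differences in rate go into the residual, where they are averaged over all the troughs as if each were fresh evidence.

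Time to steady state is a declared secondary objective, and these slopes with their 90% intervals are its only formal inferential output. If the intervals are too narrow, the report overstates how precisely the rise was measured. Readers comparing successive windows will then see intervals that clear zero more sharply than the data justify.

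**Working it through.** **Inputs from the documents.** Half-life about 90 h (Protocol 4.1). One compartment, first-order absorption and elimination (Protocol 2.2.1). Projected AUC 22.7 µg·h/mL at 50 mg (Protocol Table 11). Between-participant CV 25, 35 and 50% (Protocol 9.5). 7 active per cohort. Trough days 2, 3, 4, 6, 8 and 10–15 in Cohorts 3 and 4.

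**Assumed, because neither document gives them.** ka 0.5/h; proportional residual CV 5–30%.

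**Step 1: reproduce the plan's own figure.** Protocol 4.1: "Due to the observed half-life of ~90 h, the anticipated accumulation ratio following repeated daily and weekly doses is ~6-fold and 1.3-fold, respectively". With k = ln 2/90 = 0.00770 per h, 1/(1 − e^(−kτ)) is 5.93 for τ = 24 h and 1.38 for τ = 168 h. The daily figure matches and the weekly one is close, so the PK inputs are usable.

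**Step 2: what the model does with slope differences.** Let n = 7 participants have m troughs each, between-participant slope variance ω², residual variance σ², and Sxx the sum of squared day deviations. Leaving curvature aside:

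- true variance of the mean slope = (ω² + σ²/Sxx)/n
- variance reported by the intercept-only model = (σ²/Sxx + ω²·(n − 1)/(nm − n − 1))/n

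The model therefore counts only the fraction (n − 1)/(nm − n − 1) of ω².

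| Window | m | Sxx | Residual df (7m − 8) | Share of ω² counted |
|---|---|---|---|---|
| Days 2–15 | 11 | 210.9 | 69 | 6/69 = 0.09 |
| Days 8–15 | 7 | 34.9 | 41 | 6/41 = 0.15 |
| Days 12–15 | 4 | 5.0 | 20 | 6/20 = 0.30 |

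Sxx falls 42-fold from the first row to the last (210.9/5.0). In the last window σ²/Sxx therefore dominates and the omission of ω² matters little. In the long window the reverse holds.

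**Step 3: one case in numbers.** CL/F = 50/22.7 = 2.20 L/h and V/F = 2.20/0.00770 = 286 L. With CL/F CV 25%, participants' own Days 2–15 slopes have an SD of about 0.0131 µg/mL/day. From that source alone the SE of the mean slope is 0.0131/√7 = 0.0050, and the 90% half-width on 6 df is 1.943 × 0.0050, or about 0.0096. At residual CV 10% the intercept-only half-width averages 0.0046, about half that, and the interval covers the population mean slope in 62–64% of simulated trials.

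**Step 4: coverage by simulation.** Troughs were generated by superposition of doses, with 7 participants per trial and thousands of trials per scenario. The intercept-only interval used its balanced-data closed form (pooled within-participant slope, SE = √(MSE/(n·Sxx)), t on nm − n − 1 df). This matched a fitted mixed model for slope and SE.

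| Window | Intercept-only coverage of nominal 90% |
|---|---|
| Days 2–15 | about 42–84% |
| Days 8–15 | about 55–91% |
| Days 12–15 | about 82–91% |

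An interval built on per-participant slopes (6 df) covers about 86–91% throughout. With variability on CL/F only and the Cohort 3–4 days, the first row is about 43–82%. The slightly wider ends come from placing variability on bioavailability, or on clearance and volume together, and from Cohort 5's longer schedule.

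**Step 5: control.** With no between-participant variability, intercept-only coverage over all days is 95–99%, because curvature in the mean rise inflates the residual. The shortfall therefore comes from participant-specific rises.

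**Step 6: log scale.** Over all days, log-trough coverage is 99–100% if variability is in bioavailability, 81–96% if in clearance, and 69–90% if in clearance and volume.

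**The case against.** Several points on the other side stand. The longest windows exclude zero in essentially every simulated trial under either method, so narrow intervals change no conclusion there. The final window, on which the SAP rests its last assessment, is near nominal. A too-narrow interval delays a steady-state call, which is the cautious direction. The section does not forbid a random slope, and its residual checks could prompt a log transformation that lessens the problem. The objective is secondary, the protocol tests no hypotheses, and individual troughs will be plotted.

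What remains is the middle. Over Days 8–15 at residual CV 20%, about 18% of intercept-only intervals reach zero, against 26–31% of the per-participant ones. The planned diagnostics look at normality and constant variance, not at whether participants' slopes differ, and Step 6 shows that transformation is not a reliable cure.

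A reader might go further in three ways that the documents do not support.

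- That all troughs are treated as independent: a random intercept does give equal correlation within a participant. Only departures from the common slope are treated as independent.
- That the long half-life makes the residuals serially correlated: carry-over applies to true concentration deviations, not to the proportional residual error in the protocol's population model.
- That the intervals would falsely signal a rise at true steady state: the cohorts receive 14 or 18 daily doses and do not fully reach that state. The inflation would also need dose-to-dose variation in bioavailability, which neither document quantifies. The statement that "25% is a conservative estimate for percent within subject coefficient of variation" concerns Cmax and AUC for Part 3 precision.

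**Conclusion.** The point holds as one of misstated precision. On its ordinary reading, SAP 8.1.5.1.3 reports 90% slope intervals that are too narrow in the long and middle windows, because it omits participant-specific slopes that the protocol's own population model implies. No single coverage figure can be read from the documents. The ranges in Step 4 rest on the assumed ka and residual CV, and on the untransformed scale. The practical consequence is mainly in the middle windows. Severity is minor to moderate: a descriptive secondary objective, but a stated analysis with wrong error bars and an inexpensive remedy.

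**What to change.** In SAP 8.1.5.1.3, for each window in Cohorts 3 to 5, compute each participant's least-squares slope. Report the mean slope with a 90% t-interval on (participants − 1) degrees of freedom. Alternatively, add a random day slope by participant with Kenward-Roger degrees of freedom, and use the per-participant-slope interval if that model does not converge. State the scale of analysis.

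This takes a sentence of wording and little programming, and no new data. The cost is wider intervals: about 1.4- to 3-fold over Days 2–15 and about 10–35% in the last window. Part of the latter is simply the t multiplier, 1.943 on 6 df against 1.725 on 20 df, a ratio of 1.13. More late-window intervals will then include zero while troughs are still rising. In Cohorts 3 and 4 the Day 15 trough is 336/90 = 3.7 half-lives after the first dose, or 1 − 2^(−3.73) = 92% of plateau. The SAP should therefore also state that an interval including zero is not by itself evidence of steady state.
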